6.4 Immunogenicity and Colonization Assessments

Immune measurements will be conducted on serum (IgG and IgA) and nasal mucosal secretion (S-IgA) samples for anti-pertussis antibodies of WCE, PT, FHA, and PRN as well as any additional anti-pertussis antibodies included in assay development. Serum bactericidal activity (or other functional assays identified) will be measured in a subset of subjects.

Cellular-mediated response to BPZE1 and Boostrix (Th1/Th17 vs Th2) will be assessed by ELISpot or flow cytometry at baseline and Day 8 (safety lead-in cohort) and Day 85 and Day 113 (subset of substudy subjects). Additional testing for antigens specific to *B. pertussis* may be performed at a later date as BPZE1 induces broader immunity more similar to natural infection induced immunity and does not contain the purified antigen levels of PT, FHA, and PRN found in Boostrix. Mid-turbinate/nasopharyngeal samples will be evaluated by real-time PCR or by *B. pertussis* culture for colonization of BPZE1.

Subjects will consent for the use of samples for further anti-pertussis antibody testing or other assay development as part of the standard consenting process. Aliquots of collected samples from this study may be retained for additional testing of biological responses (eg, antibodies, T-cell responses, microbiome) specific to future development of BPZE1 and ILiAD Biotechnologies' *B-Tech* program for a maximum of 15 years (starting from the date at which the last subject had the last study visit), unless local rules, regulations, or guidelines require different time frames or different procedures, and in accord with subject consent.

Procedures for the handling and processing of immunogenicity samples are provided in the laboratory manual or the site manual.

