2.2.4. Serum Immunogenicity (IgA and IgG)

- To demonstrate that BPZE1 (BPZE1, BPZE1 + Boostrix) induction of serum immunity is significantly greater than baseline at Day 29.
- To demonstrate that BPZE1 + Boostrix induction of serum immunity is non-inferior compared to Boostrix at Day 29 (BPZE1 + Boostrix vs Boostrix).
- To demonstrate that BPZE1 (BPZE1, BPZE1 + Boostrix) induction of serum immunity remains significantly greater than baseline over the course of the study and at Day 169/EOS and to assess antibody decay curves for BPZE1, BPZE1 + Boostrix and Boostrix.
- To demonstrate that BPZE1 induction of serum IgA is non-inferior to Boostrix at Day 169/EOS (BPZE1 vs Boostrix; BPZE1 + Boostrix vs Boostrix)
- To assess if age, time since last aP vaccination (prior to study entry), or other baseline demographics have a differential response to BPZE1 or Boostrix at Day 29 (BPZE1, BPZE1 + Boostrix, Boostrix).
- To assess if baseline antibody values, by baseline quantile, have variable serum immunity responses at Day 29 when BPZE1 is given alone or with Boostrix or Boostrix alone (BPZE1, BPZE1 + Boostrix, Boostrix).
- To demonstrate that BPZE1 (BPZE1, BPZE1 + Boostrix) induces a measurable functional antibody response (subset of subjects) at Day 29; and to assess whether there is similar magnitude as that seen with Boostrix (BPZE1 vs BPZE1 + Boostrix vs Boostrix).
- To assess for seroconversion at Days 29 and 85 (BPZE1, BPZE1 + Boostrix, Boostrix). Additional combinations of antibody response (WCE, PT, FHA, PRN) may also be tested.

- To assess reverse cumulative distribution curves for immune responses (IgA and IgG) at Day 29.

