Immunogenicity endpoints (seroconversion, GMT/GMC/GMR, and GMFR) will be summarized by baseline PRN negative and PRN positive status, by quantiles of each anti-pertussis antibody (WCE, PT, FHA, PRN, and any additional anti-pertussis antibodies) and by antibody type (eg, S-IgA, IgA, and IgG separately), by the 2 age groups (6 to 10 years and 11 to 17 years, inclusive) and across age groups. An additional age group of 10 to 17 years will be added for some analyses to be able to support a rationale for immunobridging to adults. A forest plot will be generated for subgroups.

The substudy analysis will assess immunogenicity endpoints at baseline and Days 85 and 113 (independently for substudy subjects) and relative to colonization status (colonized/non colonized) at either or both Day 92 and/or 99 following re-vaccination/attenuated challenge at Day 85.

All statistical tests will be 2 sided at 0.05 significance level.

If a substantial number of subjects receive a COVID-19 vaccine that is under an emergency use authorization only, then safety analysis may also assess any AEs that may be confounded by such concomitant vaccine administration during the study.

All data collected will be listed in data listings.

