of serum IgA and IgG is non-inferior to Boostrix at Day 85 and Day 169/EOS. An ANCOVA model that includes baseline IgA or IgG and treatment group as covariates will be used to compare the natural log-transformed GMCs at Day 85 and Day 169/EOS between either BPZE1 or BPZE1+Boostrix and Boostrix groups. The non-inferiority margin is set at a 2-fold decrease or -0.693 on natural log scale. Non-inferiority will be demonstrated if the lower limit of the 95% CI of group difference on natural log scale is greater than -0.693.

Subgroup analysis by age group (6-10 years and 11-17 years, inclusive, and 10 – 17 years [for requested analyses]), time since last aP vaccination prior to study entry (<median time, \geq median time), or other baseline demographics, and by baseline antibody level (by quantile) will be conducted to examine differential responses to induction of serum immunity (IgA, IgG) at Day 29 by treatment group (BPZE1, BPZE1+Boostrix, and Boostrix). In addition to descriptive summaries, a forest plot of the corresponding 95% CIs will be generated for each subgroup.

To compare BPZE1 and BPZE1 + Boostrix induction of measurable functional antibody (subset of subjects) with Boostrix at Day 29, separate two-sample t-tests will be used to compare between treatment group differences in natural log-transformed GMC at Day 29. The corresponding 95% CIs by treatment group will be calculated on the natural log scale, then both lower and upper limits will be exponentiated to get the 95% CIs on the original scale.

Seroconversion rates with 95% CIs for IgA and IgG will be calculated at Days 29 and 85 by treatment group and day. The 95% CI will be calculated by using Agresti-Coull method. The likelihood ratio chi-square test will be used to compare seroconversion rate between treatment groups. Additional combinations of antibody response (WCE, PT, FHA, PRN, and any additional anti-pertussis antibodies) may also be tested.

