The number and proportion of subjects with a $\geq 2x$ increase from baseline in SBA bactericidal titer (50% killing titer) will be summarized by treatment group, by timepoint and by strain. The 95% CIs for each treatment group will be computed using the Agresti-Coull method and the 95% CIs for the difference in proportions between groups (BPZE1 vs Boostrix, BPZE1 + Boostrix vs Boostrix) will be computed using Agresti Caffo method. A chi-square test will be performed to compare the proportion of subjects between groups (BPZE1 vs Boostrix, BPZE1 + Boostrix vs Boostrix) with a $\geq 2x$ increase in SBA bactericidal titer and two-sided p-value will be provided.

Reverse cumulative distribution curves will be provided for SBA (PRN+ and PRN-) at baseline, Day 29 and Day 113.

9. Safety Analysis

Unless otherwise specified, safety analysis will be performed based on the Safety Analysis Set. Safety analysis for safety lead-in cohort will be performed based on the Safety Lead-in Analysis Set. All summaries and analyses will be presented by treatment groups (BPZE1, BPZE1 + Boostrix, Boostrix), age group, and overall for first study vaccination and following re-vaccination/attenuated challenge (substudy) separately.

9.1.Solicited Adverse Events

The number and percentage of subjects with any solicited AEs (local, nasal/respiratory, and systemic reactogenicity events) through 7 days following first study vaccination with any

combination of pertussis-containing vaccines (BPZE1, BPZE1 + Boostrix, Boostrix) will be calculated by treatment group, age group and overall, and by timepoint.

Solicited reactogenicity events occurring from the time of study vaccination on Day 1 for 7 consecutive days starting the day following study vaccination, including local, nasal/respiratory reactions and systemic reactogenicity, will be summarized as presenting both the number and frequency, categorized by the severity grades according to respective reactogenicity grades (Table 9-1-1, Table 9-1-2, and Table 9-1-3).

Additionally, solicited AEs will be analyzed by determining the maximum severity through 7 days following study vaccination on Day 1 to summarize the frequency and percentage of subjects reporting each local, nasal/respiratory, or systemic event.

Redness measurements, swelling measurements, and oral temperature if subjects have fever for 7 days following vaccination will be summarized using descriptive statistics.

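### The Day 29 functional-antibody comparison with Boostrix asks about similarity but is analysed by unadjusted tests of difference, with no margin or decision rule, in a subset of unstated size

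*SAP*

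**What the plan says.** The objective in SAP 2.2.4 (also Protocol 2.2) has two parts. The first is to show that BPZE1, alone and with Boostrix, produces functional antibody at Day 29 in a subset. The second is "to assess whether there is similar magnitude as that seen with Boostrix (BPZE1 vs BPZE1 + Boostrix vs Boostrix").

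For the comparison with Boostrix, SAP 8.3.2 says that "separate two-sample t-tests will be used to compare between treatment group differences in natural log-transformed GMC at Day 29". The next sentence adds intervals: "The corresponding 95% CIs by treatment group will be calculated on the natural log scale", then exponentiated. SAP Section 4 sets the level: "All statistical tests will be 2 sided at 0.05 significance level". Protocol 6.4 says only that "Serum bactericidal activity (or other functional assays identified) will be measured in a subset of subjects"; neither document gives the subset's size.

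The IgA and IgG comparisons with Boostrix in the same SAP section are handled differently. They are baseline-adjusted ("An ANCOVA model that includes baseline IgA or IgG and treatment group as covariates will be used") and have a criterion to meet ("The non-inferiority margin is set at a 2-fold decrease or -0.693 on natural log scale").

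SAP 8.4.3, in the substudy part, shows that serum bactericidal activity (SBA) is expected at baseline as well as Day 29: "Reverse cumulative distribution curves will be provided for SBA (PRN+ and PRN-) at baseline, Day 29 and Day 113".

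**The concern.** The question is about similarity and the tool is a test of difference. A non-significant p-value is compatible with equal titres and with a substantial deficit, and it becomes more likely as the subset gets smaller or the assay noisier. With no margin or stated rule for interpretation, a reader of the study report could take non-significance as evidence that BPZE1 matches Boostrix on bactericidal activity.

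Two smaller gaps go with this. The test ignores baseline titre, although the SAP plans to report baseline SBA and adjusts for baseline in the neighbouring IgA/IgG comparisons. And the first part of the objective, a rise over baseline, cannot be answered by comparing Day 29 values with an active control. The SAP's paired tests at Day 29 for serum name only IgA and IgG.

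**Working it through.** **Inputs.** Evaluable number per arm in the whole study: 108 (SAP 4.1). ln-scale SDs and mean differences for IgG: SAP Table 4-2. Test level: two-sided 0.05 (SAP Section 4). Not in the documents, so assumed: subset size (10 to 60 per arm, with 108 as the ceiling) and the SD of the functional assay (the three IgG SDs as stand-ins). A true ratio of 0.5 is used because it is the SAP's margin elsewhere; the documents set none for this assay.

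**Step 1: reproduce the plan's own figures.** No power is stated for functional antibody, so the check is on Table 4-2. SE = SD × √(2/108), noncentrality = (mean difference + 0.693)/SE, one-sided 0.025, 214 degrees of freedom.

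| IgG | Distance to margin | SE | Noncentrality | Power here | Table 4-2 |
|---|---|---|---|---|---|
| PT | −0.234 + 0.693 = 0.459 | 0.119 | 3.85 | 96.95% | 97.0% |
| FHA | −0.019 + 0.693 = 0.674 | 0.111 | 6.07 | 100% | 100% |
| PRN | −0.075 + 0.693 = 0.618 | 0.195 | 3.16 | 88.25% | 88.2% |

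The method agrees with the sponsor's.

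**Step 2: chance that the planned t-test is non-significant when the true titre is half that of Boostrix.** Noncentrality = 0.693/(SD × √(2/n)), with 2n − 2 degrees of freedom. Example at n = 20 and SD 0.8759: SE = 0.8759 × 0.3162 = 0.277, noncentrality = 2.50, critical t = 2.024, chance of non-significance 32%.

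| n per arm (assumed) | SD 0.82 | SD 0.88 | SD 1.44 |
|---|---|---|---|
| 10 | 56% | 61% | 82% |
| 15 | 39% | 45% | 75% |
| 20 | 26% | 32% | 68% |
| 30 | 10% | 15% | 55% |
| 40 | 4% | 6% | 43% |
| 60 | 0.4% | 1% | 25% |
| 108 | 0% | 0% | 6% |

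**Step 3: how low an observed ratio can be and still be non-significant.** This is exp(−t × SE). At n = 20 and SD 0.8759: exp(−2.024 × 0.277) = 0.57. For SD 0.82 and 1.44 it is 0.59 and 0.40.

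**Step 4: the opposite error.** At 108 per arm, a true ratio of 0.75 is declared different 73%, 67% and 31% of the time (SD 0.82, 0.88, 1.44), although it lies inside a 2-fold margin. Significance therefore does not answer the question in either direction.

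**Step 5: what a criterion would need.** If the lower 95% limit must exceed −0.693, a true ratio of 0.5 passes 2.5% of the time. At a true ratio of 1, n = 2 × SD² × (1.96 + 0.842)²/0.693² gives 22, 26 and 68 per arm for 80% power. A two-sided criterion (95% CI within 0.5 to 2.0) has, by simulation, 80%, 71% and 2% power at 30 per arm.

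**The case against.** - A reader might infer that the sponsor will treat non-significance as proof of similarity. No text says so. The objective says assess for magnitude, while the non-inferiority objectives in the same list say demonstrate. The plan also provides 95% CIs. This stands: the risk is one of misreading. The CIs help only if they are for the between-group ratio, which the phrase by treatment group leaves unclear, and no limit is set for them.
- A reader might infer that the t-test is the only functional-antibody analysis and that induction goes untested. SAP 8.4.3 also plans the proportion with at least a 2-fold SBA rise from baseline, compared with Boostrix using Agresti-Caffo intervals and a chi-square test. Protocol 7.4.3.2 applies the paired approach of 7.4.1.1 to secondary serum endpoints generally, and the SAP overrides the protocol only where they conflict. Much of this stands. But the responder analysis sits in the substudy part and has no margin, the McNemar tests there do not compare Day 29 with baseline, and the SAP names no paired functional-titre test at Day 29.
- The SAP does not use −0.693 for every serum comparison with Boostrix. Diphtheria and tetanus use −0.1 on proportions, and seroconversion has no margin. BPZE1 alone against Boostrix has a serum margin only at Days 85 and 169/EOS. Correct; it is therefore not an automatic choice for this assay.
- The miss rates rest on assumed sizes and on SDs for binding antibody taken from an adult study. Correct. At 40 or more per arm with an SD of 0.88 or less, the risk is 6% or lower.

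**Conclusion.** The point holds as a mismatch between question and test, with an avoidable loss of baseline information. A true halving could go undetected 26–68% of the time at 20 per arm, 10–55% at 30 and 4–43% at 40, over stand-in SDs of 0.82 to 1.44. Both the subset sizes and those SDs are assumptions, so the documents do not support calling the risk large or small without them.

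It is also tempting to conclude that importing the −0.693 limit would settle similarity. It would not. A lower limit above −0.693 shows only that the response is not less than half of Boostrix, so a several-fold higher titre would also pass, and the documents give no basis for using a binding-antibody margin for a bactericidal assay.

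This is one secondary endpoint in a subset; the study's success criterion in SAP 8.1 is unaffected.

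**What to change.** In SAP 8.3.2:

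1. Replace the t-tests with ANCOVA of Day 29 ln functional titre on treatment and baseline ln titre, as for serum IgA/IgG. Report the between-group GMC ratio with its 95% CI, and say that the CI is for that ratio.
2. State that similarity will not be inferred from a non-significant p-value. Either judge the CI against a pre-specified and justified margin, two-sided if similarity is to be claimed, or label the comparison descriptive. State the subset size so that the choice can be checked against Step 5.
3. State a paired test of Day 29 against baseline ln functional titre in the BPZE1 and BPZE1 + Boostrix groups.

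The cost is SAP wording. Baseline blood is collected from all subjects, and baseline and Day 29 SBA results are already planned in SAP 8.4.3. Because that section concerns the substudy, the sponsor should confirm that baseline is assayed for everyone in the Day 29 subset. The downside is that in a small subset the similarity conclusion may be inconclusive.

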8.4. Analyses of Endpoints for the Optional Substudy

8.4.1. Analysis of Colonization Endpoints

Colonization summary tables will be produced based on the sample type (mid-turbinate swab and nasopharyngeal swab).

The analyses in this section of the colonization substudy will be based on the PP immunogenicity analysis set but include only subjects who are enrolled in the optional open-label substudy. A sensitivity analysis will be conducted using the Immunogenicity Analysis Set but include only subjects who are enrolled in the optional open-label substudy.

To assess if prior BPZE1 induced mucosal immunity substantially reduces colonization at Days 92 and 99, the proportion of subjects with colonization at Day 92 or Day 99 will be analyzed. The 2-sided 95% CI in the proportion of subjects with colonization at either Day 92 or Day 99 (*B. pertussis* culture or PCR) will be calculated using Agresti-Coull method and summarized by treatment groups (BPZE1, BPZE1 + Boostrix, BPZE1 and BPZE1 + Boostrix, Boostrix control). The likelihood ratio chi-square test will be used to compare the proportions between treatment groups.

Separate relative risks, which are defined as the ratio of two treatment group proportions, will be calculated for 1) BPZE1 vs. BPZE1 + Boostrix; 2) BPZE1 vs. Boostrix control; 3) BPZE1 + Boostrix vs. Boostrix control; 4) BPZE1 and BPZE1 + Boostrix vs. Boostrix control. The CI for relative risk will be computed using the likelihood ratio method.

The relative risk reduction (RRR) is defined as $RRR (\%) = (1 - RR) \times 100$. The CI for the RRR will be obtained by transforming the CI for the relative risk using $(1 - UL, 1 - LL)$, where UL denotes the upper limit of the CI for the RR and LL denotes the lower limit of the CI for the RR.

The hypotheses for the primary endpoint are:

H0: RRR $\leq 0\%$

HI: RRR $> 0\%$

Rejection of the null hypothesis demonstrates a statistically significant vaccine effect, (i.e., LL of the CI $> 0\%$), and will be considered to meet the pre-specified study success criterion.

Colonization at Day 8 safety lead-in group will be analyzed to determine specimen type. Colonization at Day 29 or Day 85 will be analyzed for clearance of BPZE1.

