enrolled subject who does not receive Boostrix during the study will be offered Boostrix at the conclusion of the study (following unblinding); this Boostrix ‘catch-up’ will be provided outside of the study schedule, at the discretion of the investigator, with vaccine provided by the sponsor.

Nasal and blood samples for immunogenicity assessments will be collected before vaccination and at selected time points following study vaccination. Mid-turbinate/nasopharyngeal sample collections will occur at selected time points following study vaccination to assess initial colonization (safety lead-in cohort only, Day 8) and to assess for clearance (remainder of cohort, either Day 29 or Day 85). A subset of subjects will also have the option to provide extra blood for cellular-mediated immunity assessments at baseline and Day 8 (safety lead-in cohort) and Days 85 and 113 (subgroup optional in substudy).

Due to the uncertainty with movement and/or isolation practices associated with the COVID-19 pandemic, telemedicine and remote sampling may be initiated with proper investigator and/or medical oversight.

The primary database lock will occur after all data are clean and all planned study procedures through Day 169/EOS (6 months) are complete. An interim database lock may occur after all subjects have completed Day 29 and sample testing for all primary and select secondary immune endpoints have been completed (mucosal and serum), but results will only be provided at treatment assignment level to maintain the blind. The site and those interacting directly with the site or subject data (eg, contract research organization [CRO], laboratories) will remain blinded to subject assignment until EOS or end of sample testing, depending on the activities of the associated entities.

Vaccination pause rules (refer to Section 6.5) will be in place with a review by the SMC initiated if any rule is met. In addition, the medical monitor and medical lead are empowered to request a review by the SMC (refer to Section 11.1.1.1) at any time for any safety reason.

3.1.1 Substudy: Attenuated Challenge With BPZE1 Following Prior Vaccination with BPZE1, BPZE1 + Boostrix, or Boostrix Alone

This is an optional open-label substudy in which enrolled subjects may elect to participate at any time from the day of enrolment through Day 85. A separate signed ICF (and separate

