3.2.2.5. Safety

Subjects participating in the substudy will be evaluated for safety endpoints in a separate evaluation after Day 85 re vaccination/attenuated challenge.

- Maximum daily severity during the 7 days following study vaccination (by treatment group).
- Incidence by toxicity grade during the 7 days following study vaccination (by treatment group).
- Mean response (for any measurements) and duration during the 7 days following study vaccination (by treatment group).
- All AEs through 28 days following study vaccination by severity and relationship to study vaccination (by treatment group).

- All MAAEs through 84 days following study vaccination by severity and relationship to study vaccination, and by time since study vaccination (by treatment group).
- All AESIs and SAEs through Day 169/EOS by severity and relationship to study vaccination, and by time since study vaccination (by treatment group).
- Incidence of SARS-CoV-2 infections or AESIs associated with COVID-19 disease by severity, and by time since study vaccination (by treatment group).
- *B. pertussis* clearance following study vaccination (subset of subjects at varying time points through Day 85).

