4.3.4. Per-Protocol (PP) Immunogenicity Analysis Set

Immunogenicity Analyses to be performed based on PP Immunogenicity Analysis Set.

The PP immunogenicity analysis set will consist of all subjects in the immunogenicity analysis set, with the following exclusions:

- Data from all available visits for subjects following the receipt of unsuitable investigational product (either via dispensed and/or assigned or delivered).
- Data from all available visits for subjects found to be ineligible at baseline per protocol.
- Data from all subjects who received at least one dose of whole-cell pertussis (wP) containing vaccine in their life.
- Data from all available visits for subjects following the use of major immune modulators or immunosuppressants or following the receipt of blood products.
- Data from all available visits for subjects following clinically significant protocol deviations that can affect the efficacy (immunogenicity) results as determined by clinical review.

- Data from any visit that occurs substantially out of window as defined by exceeding 30 days past the visit window or the time point whereby the follow-up visit should have occurred, whichever is most restrictive.
- For subjects in the colonization substudy, missing Day 92 and Day 99 cultures will be removed from the Colonization endpoint.

For analyses using the PP immunogenicity analysis set, subjects will be classified according to the randomized treatment group. Determination of exclusions from the PP Immunogenicity Analysis Set will be performed by the sponsor clinical lead in a blinded fashion prior to the database lock.

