4.4. Handling of Missing Data

Impute Missing Colonization Data

Colonization data will be presented in the listings as reported for subjects consented to substudy only. For summaries and analysis, the following conventions apply.

When only one day out of two days (Day 92 or Day 99) is missing:

- If Day 92 is negative but Day 99 is missing, Day 99 will be imputed as negative;
- If Day 92 is missing but Day 99 is negative, Day 92 will be imputed using fully conditional specification multiple imputation.
- If any day is positive, the remaining missing data will not be imputed.

When subjects drop out before they visit on Day 92 but consent to the substudy, i.e., all two days (Day 92 and Day 99) are missing:

- Status of being positive or negative for a given day will be imputed using fully conditional specification multiple imputation.

Multiple imputation method for missing binary outcome of colonization

Imputation of the missing binary variable of being a colonizer or non-colonizer will be done using fully conditional specification with a logistic model. The multiple imputation procedure and the analysis will be conducted in three separate steps: 1) Imputation 2) Analysis of imputed complete data sets 3) combination of results using Rubin's rule.

1. Imputation (using SAS PROC MI): Use the logistic method with age group as covariate to impute the missing colonization status of being positive or negative by treatment group. The FCS LOGISTIC statement will be used with a seed of 57808563. In this MI approach, SAS® procedure PROC MI performs MI by replacing each missing value with a set of plausible values by treatment group. The missing data will be filled in multiple times to generate multiple complete data sets. The number of imputed complete data sets will be 50.
2. Analysis of imputed complete data sets: imputed data sets will then be analyzed separately using the same method for the colonization endpoint as described in [Section 8.4.1](#).
3. Combination of estimates across imputed datasets (can be obtained using SAS PROC MIANALYZE): the results obtained from Step 2 (one for each imputation), which are difference in response proportion and its standard errors, will then be combined per Rubin's rule (t statistics and standard errors), p-values for combined t-statistics will be derived using Student's t distribution with error degrees of freedom.

Impute Missing Adverse Events/ Prior or Concomitant Medications

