8.3. Secondary Endpoints Analyses

Unless otherwise specified, data will be summarized for each endpoint as described in [Section 3.2](#). Listings will be provided for all data as collected.

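### The SAP's only explicit analysis of BPZE1 clearance, a main-study safety endpoint, sits in a section limited to substudy enrolees; read literally it drops more than half of the clearance swabs from BPZE1 recipients

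*SAP*

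**What the plan says.** SAP 3.2.2.5 lists *B. pertussis* "clearance following study vaccination (subset of subjects at varying time points through Day 85") among the secondary safety endpoints. Protocol 3.1 takes the swabs "to assess for clearance (remainder of cohort, either Day 29 or Day 85"), and footnote u of the schedule of events (Protocol Table 13-1, SAP 13.1) randomises children outside the lead-in cohort 1:1 between those two days.

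The SAP's analysis is one sentence at the end of Section 8.4.1: "Colonization at Day 29 or Day 85 will be analyzed for clearance of BPZE1". It names no method, denominator or analysis set of its own. Section 8.4.1 falls under the heading for optional-substudy endpoints, and its analyses are "based on the PP immunogenicity analysis set but include only subjects who are enrolled in the optional open-label substudy". The alternative set is no wider: "A sensitivity analysis will be conducted using the Immunogenicity Analysis Set but include only subjects who are enrolled in the optional open-label substudy". SAP 4.4 adds: "Colonization data will be presented in the listings as reported for subjects consented to substudy only".

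Other text is broader. SAP 8.3 says: "Unless otherwise specified, data will be summarized for each endpoint as described in" Section 3.2, which includes clearance. SAP Section 9 makes the Safety Analysis Set the default for safety analyses. SAP Section 4 and SAP 8.3 both promise listings of all collected data. Protocol 7.4.3.3 plans a number and percentage with colonization or clearance and states no substudy limit.

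**The concern.** The sampling plan spreads clearance swabs over the whole non-lead-in cohort, but the one sentence that analyses them sits under a restriction to an opt-in minority. The Day 92 and Day 99 swabs cannot make up the loss, because they follow a second BPZE1 dose and do not inform clearance of the first.

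This is the first BPZE1 study in school-age children. The protocol's statement that long-term colonization is not expected rests on earlier studies, so this endpoint is where the trial itself would show whether the strain persists. A self-selected subset would give a much less precise answer. Even if the restriction was not meant to reach the clearance line, that line then has no stated population, and two programmers could produce different tables from the same data.

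**Working it through.** The documents give no count of clearance swabs, so there is no plan figure to reproduce. The counts below are built from stated inputs.

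**Inputs.** 360 children randomised 1:1:1, two of the three arms receiving BPZE1; 45 in the lead-in cohort, who are outside the Day 29/85 assignment; clearance swab day assigned 1:1; substudy capped at 120 (SAP 3.1, SAP 13.1 footnote u). Assumptions: the substudy fills, and uptake is even across arms.

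**Base counts.**
- BPZE1 recipients outside the lead-in: (360 − 45) × 2/3 = 210, so 105 are assigned to each swab day.
- Of these, in the substudy: 120 × 2/3 × 315/360 = 70 if uptake is proportional, or 120 × 2/3 = 80 if no lead-in child joins.

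**Day 85 swabs in substudy children.** The documents allow three readings:
- A: the schedule cell for the substudy Day 85 visit (SSV3) is blank, so no swab is taken.
- B: footnote u has no substudy exception, so each child keeps the assigned day.
- C: Protocol 3.1.1 and SAP 3.1 have substudy children contribute to all Day 85 sampling, nasal included, so all are swabbed that day.

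| Reading | Swabs from BPZE1 recipients | Kept under 8.4.1 | Left out | Left out if no lead-in child joins | Day 85 swabs kept |
|---|---|---|---|---|---|
| A | 105 + 70 = 175 | 35 | 140/175 = 80.0% | 130/170 = 76.5% | 0 of 70 |
| B | 105 + 105 = 210 | 35 + 35 = 70 | 140/210 = 66.7% | 130/210 = 61.9% | 35 of 105 |
| C | 105 + 140 = 245 | 35 + 70 = 105 | 140/245 = 57.1% | 130/250 = 52.0% | 70 of 140 |

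**Sensitivity.**
- Lower uptake (proportional): at 90 substudy children, A, B and C leave out 85.7%, 75.0% and 66.7%; at 60, they leave out 90.9%, 83.3% and 76.9%.
- Per-protocol loss: an assumed 10% loss moves 80.0% under A to 1 − 0.9 × 35/175 = 82.0%.
- Uneven uptake: in the extreme where all 120 are BPZE1 recipients outside the lead-in, the share left out falls to 1 − 60/150 = 60.0% under A and 1 − 120/210 = 42.9% under B. "More than half" therefore depends on a roughly even split. That is plausible because subjects are blinded when they opt in, but it is not guaranteed.

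**Precision at Day 29.** With proportional uptake, 35 of 105 swabs are kept under all three readings. With no positives, the one-sided 95% upper bound on carriage is 1 − 0.05^(1/n): 8.2% for n = 35 and 2.8% for n = 105. If true carriage were 2% (an assumption; the documents give no rate), the chance of seeing at least one carrier is 1 − 0.98^n: 51% against 88%.

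**The case against.** The strongest reply is that the restriction was never meant to cover the clearance line. It is worded for analyses of the colonization substudy. The sentence just before the clearance line concerns Day 8 swabs in the lead-in group, which cannot sensibly be limited to substudy enrolees. Under the blank-cell reading, the restriction would leave the Day 85 half of the clearance sentence with no data. The general clauses in SAP 8.3 and Section 9 and the summary in Protocol 7.4.3.3 would then supply a main-study analysis. The 4.4 listing sentence appears under imputation rules for Days 92 and 99.

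Much of this stands, and it is why certain exclusion cannot be claimed. It does not settle the matter. Both general SAP clauses yield where something else is specified, and 8.4.1 arguably specifies it. SAP Section 1 makes the SAP govern where the two documents are inconsistent. If the restriction does not apply, the clearance line has no population or method of its own.

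A reader might go further in four ways that the documents do not support:
- That every Day 85 swab is lost. This follows only from the blank SSV3 cell, which conflicts with the Day 85 sampling text and footnote u.
- That 80% is the figure. It is one reading, with a full and evenly split substudy.
- That dropping data "following the use of major immune modulators or immunosuppressants or following the receipt of blood products" hides slow clearers. The Immunogenicity Analysis Set, used for sensitivity, lacks that exclusion, and recent immunosuppressant use already bars entry. The point is minor.
- That Boostrix-only children are scored as cleared. No passage states such a rule, and safety summaries are by arm. What is true is that the SAP does not define the clearance denominator.

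**Conclusion.** The point holds as a misplaced or ambiguous analysis set for a main-study safety endpoint. The only explicit clearance analysis in the SAP stands under two sets that both admit substudy enrolees only, and SAP 4.4 limits listings in the same way, against the all-data listing text elsewhere in the SAP. Followed literally, this omits about 52% to 80% of BPZE1 recipients' clearance swabs with a full substudy of 120 split evenly across arms, before any per-protocol loss, and more with lower uptake. A split strongly weighted to the BPZE1 arms would reduce it. A wider analysis may well be intended, but the SAP does not say so. The swabs are collected either way, so the loss is confined to analysis and reporting and can be prevented in the text.

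**What to change.** - Move the clearance analysis to SAP Section 9, on the Safety Analysis Set by actual vaccine. Include every child with a valid Day 29 or Day 85 main-study swab, whether or not the child joins the substudy.
- Report the number and percentage positive by swab day and treatment arm, with Agresti-Coull intervals (already the SAP's method for proportions). Show Boostrix-only children as negative controls.
- State in 8.4.1 that the substudy restriction applies only to the Day 92 and Day 99 challenge analyses.
- Extend the SAP 4.4 listing to all colonization results, in line with SAP Section 4 and SAP 8.3.
- Reconcile the blank SSV3 swab cell with the Day 85 sampling text (Protocol 3.1.1, SAP 3.1) and footnote u.

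The cost is SAP wording and one or two tables from data already collected. The analysis change needs no new samples.
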